4.2 Inclusion criteria

In order to be eligible to participate in this study, a subject must meet all the following criteria:

- Healthy participants (defined as those without a pre-existing medical comorbidity);
- Aged between 18-65 years;
- Ability to understand and speak the Dutch language.

4.3 Exclusion criteria

A potential subject who meets any of the following criteria will be excluded from participation in this study:

- Medical history or condition affecting the cardiovascular, respiratory, urogenital, gastrointestinal/hepatic, haematologic/immunologic, HEENT (head, ears, eyes, nose, throat), dermatological/connective tissue, musculoskeletal, metabolic/nutritional, endocrine, neurological/psychiatric systems, as well as prior major surgeries or ongoing laboratory abnormalities that could potentially limit participation or completion of the study protocol;
- Any use of medication, especially those that may influence the autonomic nervous system or the hypothalamus-pituitary-adrenal axis (e.g., beta-agonists or corticosteroids), with the exception of contraceptives and paracetamol;
- Current or lifetime psychopathology (including PHQ-9 and GHD-7 scores ≥ 10);
- Substance abuse (including excessive alcohol consumption);
- Smoking;
- Pregnancy, lactation, or intention to become pregnant during the study period;
- Use of devices (e.g., cochlear implants) or other reasons (e.g. wounds, permanent ear-piercing) which complicate the use of the tVNS device;
- Participation in another clinical study in which the MAST was used;

- Administration of investigational drugs or participation in any scientific intervention study that might interfere with this study (to be determined by the principal investigator) within 180 days preceding the commencement of the study;
- Students and employees of Maastricht University are not precluded from participation, unless they have a direct personal, professional or hierarchical position with regards to any of the study team members or their department.

4.4 Sample size calculation

There are no directly comparable studies available for an accurate sample size calculation, as previous research investigating the effect of tVNS on stress used different stimuli, making comparison challenging. However, previous research on the Maastricht Acute Stress Task (MAST) indicated that 85% of participants demonstrate a noticeable and quantifiable cortisol response (i.e., cortisol increase $\geq 2.5\text{nmol/l}$ from baseline) to the acute stress task (1). Anticipating that tVNS is expected to counteract the cortisol response to the MAST by 35%, resulting in an estimated 85% cortisol increase from baseline in the sham group vs. a 50% increase from baseline in the tVNS group, a sample size of 54 participants is required to detect this difference ($b=0.8$, $\alpha=0.05$). This estimate is consistent with other somewhat similar studies on tVNS. Based on previous experience with studies involving healthy volunteers, an additional six participants (10%) will be recruited to account for potential dropouts. This approach is deemed appropriate and feasible given the short and non-invasive nature of the intervention.

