Objective: The primary aim of this study is to assess the efficacy of taVNS in mitigating the acute stress response induced by the Maastricht Acute Stress Task (MAST) among healthy subjects, measured by cortisol levels in saliva samples. It is hypothesized that taVNS will significantly reduce the cortisol response to the MAST by 35%. Since prior research showed that 85% of healthy participants exhibited a measurable cortisol response ((i.e. cortisol increase ≥ 2.5 nmol/l) to the MAST, a responder rate of 85% is expected in the sham group compared to 50% in the taVNS group (1).

Secondary objectives include evaluating taVNS's potential to counteract stress-induced sympathetic activation, thereby reducing negative affect as measured by the International Positive and Negative Affect Schedule Short Form (I-PANAS-SF), as well as feelings of stress, pain, and unpleasantness, on 0-100 Visual Analog Scales (VAS). Additionally, the study will assess taVNS's impact on autonomic outflow parameters and examine the relationship between stress responses and affective symptoms and personality trait, using the Generalized Anxiety Disorder 7-Item Scale (GAD-7), Patient Health Questionnaire (PHQ-9), and the Big Five Inventory (BFI).

Study design: This study concerns a single-centre, prospective, double-blind, randomized, placebo-controlled interventional trial with a (1:1) parallel design, with all measurements conducted at Maastricht University.

Study population: This study aims to enrol 60 healthy volunteers aged 18-65 years.

Intervention: Participants will be randomly assigned to either the taVNS or sham stimulation group, administered 30 minutes before the MAST.

Main study parameters/endpoints: The primary endpoint is a significant reduction in the neuroendocrine stress response, measured by saliva cortisol samples, in the taVNS group compared to the sham treatment group following the MAST.

Nature and extent of the burden and risks associated with participation, benefit and group relatedness:

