2. OBJECTIVES

2.1 Primary Objective

To investigate the efficacy of taVNS in attenuating the acute stress response induced by the validated Maastricht Acute Stress Task (MAST) among healthy subjects, as measured by cortisol levels in saliva samples.

Hypothesis

We hypothesize that taVNS can significantly mitigate the cortisol response to the MAST by 35%, which we assume to be a biologically relevant difference. Specifically, we anticipate a cortisol increase of 85% from baseline in the sham group compared to an 50% increase from baseline in the taVNS group. This hypothesis builds upon prior research, where 85% of participants exhibited a measurable cortisol response (i.e. cortisol increase ≥ 2.5 nmol/l from baseline) to the MAST, indicating an evident and quantifiable response to the acute stress task (1).

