10.1 Primary study parameter(s)

The efficacy of taVNS in attenuating the acute stress response induced by the validated Maastricht Acute Stress Task (MAST) among healthy subjects will be determined based on cortisol levels in saliva samples, using an intention-to-treat principle. A repeated measures ANOVA will be utilized to evaluate both intergroup differences and within-group changes in cortisol levels across the different time points. If the assumption of normality is violated, a nonparametric equivalent will be employed. Multivariable regression analysis will be performed to correct for confounding effects of age, gender, and mental health (i.e. GAD-7, PHQ-9, BFI). Differences in cortisol saliva levels, with corresponding 95% confidence intervals (CIs) and two-sided p-values, will be calculated at a type I error level of 0.05.

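### The 80% power for 54 participants fits a comparison of responder proportions (85% vs 50%), but the planned primary analysis is a repeated measures ANOVA on cortisol levels

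*Protocol*

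**What the plan says.** - **Source of the figure.** Section 4.4 takes from earlier work with the stress task that "85% of participants demonstrate a noticeable and quantifiable cortisol response", defined as a rise of at least 2.5 nmol/l. This is a proportion of people.
- **Summary, Objective.** The hypothesis is put on that scale: "a responder rate of 85% is expected in the sham group compared to 50% in the taVNS group".
- **Section 2.1.** The same two numbers become a size of response: "we anticipate a cortisol increase of 85% from baseline in the sham group compared to an 50% increase from baseline in the taVNS group".
- **Section 4.4.** The same change is made ("resulting in an estimated 85% cortisol increase from baseline in the sham group vs. a 50% increase from baseline in the tVNS group"), followed by "a sample size of 54 participants is required to detect this difference", at 80% power and alpha 0.05. Six more participants are added for dropout, giving 60.
- **Section 8.1.1.** The main endpoint is a reduction in the cortisol response with a 35% threshold. No scale and no responder definition are given.
- **Section 10.1.** "A repeated measures ANOVA will be utilized to evaluate both intergroup differences and within-group changes in cortisol levels across the different time points". A nonparametric equivalent and a multivariable regression are also mentioned, with "two-sided p-values, will be calculated at a type I error level of 0.05". Responder proportions are not compared.

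**The concern.** A proportion of participants whose cortisol rises by at least 2.5 nmol/l and a mean percentage rise in cortisol are different quantities. The first needs no SD for a sample size calculation; the second does. The protocol uses one pair of numbers for both and then plans an analysis of the continuous measurements.

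The justification for the trial's size is therefore attached to a comparison that the protocol does not plan. Someone reading the results could take a null finding as evidence, at 80% power, against a 35% reduction in the cortisol response. Nothing in the document supports that statement for the ANOVA. It is also unclear which 35% would have been excluded.

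**Working it through.** **Inputs.** 85% and 50% (Summary; sections 2.1 and 4.4); power 0.80 and alpha 0.05 (section 4.4); two-sided testing (section 10.1); 1:1 allocation (section 8.2). The document gives no SD, no within-person correlation and no expected cortisol profile.

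**1. Reproduce the 54 as two proportions**, with pooled variance under the null and no continuity correction:

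n per arm = [z(0.975)·√(2·p̄·(1−p̄)) + z(0.80)·√(p1(1−p1) + p2(1−p2))]² / (p1−p2)²

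- p̄ = (0.85 + 0.50)/2 = 0.675, and 2 × 0.675 × 0.325 = 0.43875, with square root 0.6624
- 0.85 × 0.15 + 0.50 × 0.50 = 0.3775, with square root 0.6144
- n = (1.960 × 0.6624 + 0.8416 × 0.6144)² / 0.35² = (1.298 + 0.517)² / 0.1225 = 26.9, so 27 per arm and **54 in total**
- Normal-approximation power at 27 per arm: 80.2%
- Dropout: 54/(1 − 0.10) = **60**, as stated

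The two-sided arcsine formula also gives 54, as does a one-sided test with continuity correction. Other two-sided variants give 50 (unpooled) and 66 (with continuity correction).

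**2. Try the 54 as a comparison of mean increases.** With 27 per arm, a two-sided t-test at 0.05 has 80% power for a standardised difference d of 0.777. For a 35-point difference the SD would have to be 35/0.777 = 45 percentage points. No such figure appears in the protocol, so the 54 cannot be derived on this reading.

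**3. What the power would be on the continuous scale.** The test is a two-group t-test on one summary value per person, with 27 per arm, a 35-point difference and d = 35/SD. Every SD here is an assumption.

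| Assumed SD (points) | Power |
|---|---|
| 30 | 99% |
| 40 | 88% |
| 45 | 80% |
| 60 | 56% |
| 80 | 35% |
| 100 | 24% |

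**4. Start from the responder rates instead.** Assume that the cortisol rise is normal with equal variance in both arms, and that 85% and 50% exceed 2.5 nmol/l. The means then differ by z(0.85) − z(0.50) = 1.04 SD. A t-test with 27 per arm has about 96% power for that difference.

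**5. The scale of the 35%.** 85 − 50 = 35 percentage points. Relative to 85 the reduction is 35/85 = 41%. A 35% relative reduction from 85 would end at 0.65 × 85 = 55.25, not 50.

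**The case against.** The strongest reply is that nothing has been miscalculated. The 54 and the 60 are both right for the responder rates in the Summary. If those rates hold and the response is roughly normal, a continuous analysis would have more power than the responder comparison, about 96% in step 4. Section 4.4 admits that no directly comparable studies exist for an accurate calculation. Section 10 promises effect sizes and confidence intervals and says that conclusions will not rest on one p-value, which makes a misread null result less likely.

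Most of this stands. The arithmetic is correct, and the reporting commitments soften the harm. But the favourable 96% needs a distributional assumption that the protocol does not make, and it applies to the responder hypothesis, not to the mean increases written in sections 2.1 and 4.4.

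The chi-square and Fisher tests in section 10 do not supply the missing responder analysis. They are general wording for categorical variables, in a paragraph that opens with subject characteristics. An unseen statistical analysis plan does not settle the matter either, because the protocol itself fixes the hypothesis, the calculation and the primary test, and these disagree.

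A reader might go further and infer that the trial is underpowered. The documents do not support that: without an SD, the power could lie on either side of 80%. Nor is it proved that the 54 came from a two-proportion formula. That is a strong inference, from the exact match, the Summary's responder rates and the absence of any SD.

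**Conclusion.** The concern holds as a mismatch between the endpoint used for the sample size and the primary analysis, not as an arithmetic error. The protocol states its primary effect on two incompatible scales. The 80% power matches a responder comparison that is not planned, and the 35% in the Summary and sections 2.1, 4.4 and 8.1.1 has no single meaning (35 points, or 41% in relative terms).

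These conclusions rest on the text and on step 1 alone. The power of the repeated measures ANOVA is unknown. The range of 99% to 24%, and the 96%, are illustrations under assumed SDs or assumed normality, for a single-summary t-test rather than for the ANOVA itself. They show that the stated 80% cannot be carried over to the planned analysis, not that the true figure is lower.

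**What to change.** - **Sections 2.1 and 4.4:** state that 85% and 50% are the expected proportions with a rise of at least 2.5 nmol/l, as in the Summary, and delete the wording that makes them increases from baseline.
- **Summary and section 8.1.1:** say on which scale the 35% is measured, and use that scale throughout.
- **Section 10.1:** keep the continuous analysis and name one between-group cortisol contrast as primary, for example a baseline-adjusted post-stress summary or a specified group-by-time contrast.
- **Section 4.4:** state that 54 evaluable participants give 80% power for a standardised difference of about 0.78 in a two-group comparison of a single summary value. Say that this figure applies to the named contrast if it is reduced to one value per person, and drop the claim of 80% power for a 35% reduction.
- **Section 10.2:** add the 2.5 nmol/l responder comparison, to which the 54 applies, as a named secondary analysis.

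Making responder status primary, with a two-proportion test, would also be consistent. Keeping the continuous analysis is preferred because it leaves the planned primary analysis in place.

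The cost is a protocol amendment to wording and a less favourable stated detectable effect. No extra participants are needed.

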5. TREATMENT OF SUBJECTS

This study aims to investigate the efficacy of taVNS in attenuating the acute stress response by comparing stress-related outcomes between the active and sham groups.

5.1 Investigational product/treatment

The intervention of interest is taVNS, with sham stimulation employed as the appropriate control.

5.1.1. taVNS

Electrical stimulation will be administered to the auricular branch of the vagus nerve, specifically at the cymba conchae of the right ear, using a custom-made device called tVNS R (tVNS Health GmbH, Grünwald, Germany). This device comprises a stimulation unit and an ear electrode. This electrode is connected as an anode to the stimulation device by a cable and is worn similarly to an earphone. The stimulation unit sends electrical impulses through the electrode, which stimulates the auricular branch of the vagus nerve. On the test day, subjects assigned to the taVNS group will receive 30 minutes of active stimulation before the MAST procedure. According to recent systematic analyses determining the most optimal treatment frequencies for taVNS, the stimulation parameters will consist of biphasic rectangular pulse trains with an impulse frequency of 25Hz, impulse duration of 30 seconds, followed by an impulse pause of 30 seconds, and an impulse width of 450ms (26, 27). Each participant will undergo sensory testing prior to the commencement of the treatment period during which the current will be adjusted to suprathreshold stimulation intensity, with current intensities ranging between 0.25 and 10 mA. The device will indicate stimulation delivery by blinking. Concurrently with taVNS stimulation autonomic parameters, using a blood pressure monitor, FitBit smartwatch, and a Shimmer3 GSR sensor, will be collected.

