Both taVNS treatment and sham stimulation will be administered using a tVNS device that provides stimulation to the cymba concha of the right ear. The right side is chosen based on the innervation pattern of the right vagus nerve and to ensure comparability with previous studies, such as the RESILIENCE study (NL84720.068.23 / METC 23-032). In addition, our ultimate clinical interest is related to conditions such as irritable bowel syndrome, which is considered to originate from the distal bowel. This part of the intestine is predominantly innervated by the right vagus nerve. The stimulation parameters comprise a biphasic rectangular pulse wave with an impulse frequency of 25Hz, impulse duration of 30 seconds, impulse pause of 30 seconds, and pulse width of 450ms. These parameters have been identified as the most optimal treatment frequencies for taVNS based on recent systematic reviews (26, 27). Prior to the experiment, the stimulation current will be adjusted according to the subject's sensitivity to ensure it remains below the pain threshold, with current intensities ranging between 0.25 and 10 mA. Active stimulation will be programmed in a way that it only delivers subthreshold stimuli. The device will blink when the stimulation is delivered. In the sham (control) group, the same location of the electrode will be used but the electrode will be non-conducting. The device will still blink to maintain blinding (27). Sham stimulation at a different anatomical location without vagal innervation (such as the earlobe) is considered at risk for deblinding given the information available in lay media. Nonetheless, the electrodes used in the tVNS and sham groups differ slightly. Consequently, the investigator placing the electrodes will be aware of the treatment allocation. To ensure proper blinding, two researchers will be involved on the test day. One researcher will manage the part of the tVNS stimulation and will be responsible for programming the devices, while the other researcher will conduct the second part of the test day, the Maastricht Acute Stress Task (MAST). This division ensures that the researcher conducting the MAST and responsible for data analysis is blinded to the treatment allocation.

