8.3 Study procedures

8.3.1 Visit 1

The screening visit will take place at the NUTRIM Clinical Research Unit (CRU) of Maastricht University. At this first visit, all participants will be asked to confirm that they have read the information letter, received oral information, and have no further questions regarding the study. The investigator will ensure the participant understands all the information through an interview. Afterward, the eligibility criteria will be checked, and if suitable, the participant will be asked to complete written informed consent prior to any study procedures. Following inclusion, participants will be requested to complete several questionnaires, including a baseline questionnaire (F1.1_Baseline_Characteristics_Questionnaire_Versie1.0_dd 06-06-2024), GAD-7 (F1.2_GAD7_Versie1.0_dd 06-06-2024), PHQ-9 (F1.3_PHQ9_Versie1.0_dd 06-06-2024), and BFI (F1.4_BFI_Versie1.0_dd 06-06-2024), with the support of Castor EDC. Given that current or lifetime psychopathology serves as an exclusion criterion and the GAD-7 and PHQ-9 assess for the presence of anxiety and depression disorders, respectively, participants scoring 10 or above on either questionnaire will be excluded from the study (47).

8.3.2 Visit 2

The test day will take place at the NUTRIM Clinical Research Unit (CRU) of Maastricht University. Upon arrival at the CRU, all subjects will complete a checklist to verify compliance with the test day regulations. These regulations include not eating or drinking anything except water, brushing their teeth, using chewing gum, or smoking one hour prior to the start of the test session (until the last saliva sample

has been taken). Furthermore, participants must not consume alcohol on the day before the test day, nor consume caffeine or engage in physical exertion on the day of the test session.

Once compliance is confirmed, the investigator, responsible for the first part of the test day, will have the participant complete the I-PANAS-SF questionnaire and the VAS scales. Blood pressure will then be measured, and the FitBit smartwatch and the Shimmer3 GSR sensor will be applied to allow for continuous measurement of autonomic parameters. Afterward, the sensory threshold of the tVNS device will be calculated. The tVNS device will be programmed to deliver only subthreshold stimuli to assure blinding. Subjects will then receive 30 minutes of either active taVNS or sham stimulation, followed by the MAST.

Maastricht Acute Test Task (MAST)

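### Section 5.1.1 sets the active current above threshold, while sections 3 and 8.3.2 allow only subthreshold stimulation; with a non-conducting sham, following 5.1.1 could compromise participant blinding

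*Protocol*

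**What the plan says.** Three places in the protocol state the intensity of active stimulation relative to a threshold.

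- **Section 5.1.1 (taVNS)** describes "sensory testing prior to the commencement of the treatment period during which the current will be adjusted to suprathreshold stimulation intensity", with a range of 0.25 to 10 mA.
- **Section 3 (Study design)** says: "Active stimulation will be programmed in a way that it only delivers subthreshold stimuli". It also has the current adjusted to the participant's sensitivity "to ensure it remains below the pain threshold, with current intensities ranging between 0.25 and 10 mA".
- **Section 8.3.2 (Visit 2)** gives the order of events on the test day: "Afterward, the sensory threshold of the tVNS device will be calculated"; then "The tVNS device will be programmed to deliver only subthreshold stimuli to assure blinding"; then "Subjects will then receive 30 minutes of either active taVNS or sham stimulation, followed by the MAST".

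Sections 3, 5.1.2 and 8.2 describe the sham as a non-conducting electrode at the same ear site, with a device that still blinks. The participant-blinding claims in sections 5.1.2 and 8.2 rest on the shared location, the identical device and the blinking.

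**The concern.** The protocol gives two opposite instructions for the strength of the intervention. The person programming the device could follow either section and still be complying with the protocol, and the tVNS R does not settle the matter because its parameters are adjustable (section 6).

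Two things are at stake. The first is participant blinding. If the active current is felt and the sham delivers none, sensation becomes a cue present in one arm only, and neither the location of the electrode nor the blinking hides it. Section 8.3.2 itself gives blinding as the reason for staying below threshold. The outcomes most open to expectation are the self-reported I-PANAS-SF and VAS scores. The second is the dose. If operators follow different sections, the trial's result cannot be tied to one defined stimulation intensity.

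**Working it through.** The main check is a comparison of the text; a short calculation shows how much of the treatment is affected.

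**Statements side by side**

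| Section | Intensity relative to threshold | Threshold named | Reason given |
|---|---|---|---|
| 3 | below | pain threshold mentioned nearby | none in that sentence |
| 5.1.1 | above | none, but set during sensory testing | none |
| 8.3.2 | below | sensory threshold | blinding |

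One statement says above and two say below.

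**Can the threshold meant be the pain threshold?** In section 3 taken alone, it can. In section 8.3.2 it cannot, because that section names the sensory threshold immediately before the programming step and gives blinding as the purpose. The pain limit in sections 3 and 13.1 does not remove the conflict: a current that is felt but not painful respects that limit and section 5.1.1, yet breaks section 8.3.2.

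**Can *suprathreshold* describe titration only?** Grammatically, yes. However, section 5.1.1 speaks of a stimulation intensity, attaches the same 0.25 to 10 mA range that section 3 gives for the stimulation current, and states no later reduction. It is also the section to which the device description in 6.1 refers for details, and the dosage section 6.6 is marked not applicable. The titration reading is therefore strained.

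**Extent**

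- Active arm: 60 participants at 1:1, so 60 / 2 = 30.
- Cycle, from section 5.1.1 ("impulse duration of 30 seconds, followed by an impulse pause of 30 seconds"): 30 s + 30 s = 60 s.
- On-periods in a 30-minute session: 1800 s / 60 s = 30.
- Current per active participant: 30 × 30 s = 900 s = 15 minutes.
- Current per sham participant: 0 minutes (non-conducting electrode).

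On the natural reading of section 5.1.1, all 15 minutes are above the sensory threshold; under section 8.3.2, none are. These figures show how much of the treatment the conflict covers. They do not measure unblinding or bias, for which the protocol gives no input.

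**The case against.** The strongest reply is that the intent can be recovered. Section 8.3.2 is the step-by-step procedure that staff will use, it gives a reason, and section 3 agrees with it; section 5.1.1 may be a drafting slip. That is probably right about the intent, and it identifies section 5.1.1 as the likely error. It does not make the instruction harmless, because 5.1.1 is the treatment section and reads as an order.

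A second reply is that finding a sensory threshold requires some current that is felt, so *suprathreshold* may belong to the testing step. This reading remains open, but for the reasons set out in the working it is not the natural one.

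Other points on that side stand and limit the claim:

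- The primary outcome is laboratory-assayed salivary cortisol, so assay bias is not the issue.
- Each participant has a single session and cannot compare active with sham.
- Section 13.1 attributes ear tingling to only a few subjects, so it is weak evidence for a cue across the whole arm.
- Section 3 rejected a sham at another site because it "is considered at risk for deblinding given the information available in lay media". That argument concerns location, not sensation. It shows that the protocol takes participant blinding seriously, and no more.
- Threshold testing may itself be felt, and the protocol does not say how it is done in the sham arm. Rewording section 5.1.1 therefore removes the contradiction but does not by itself guarantee blinding.

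**Conclusion.** The concern holds. Section 5.1.1 contradicts section 8.3.2, and section 3 on its plain reading, about the intensity of the active treatment. If section 5.1.1 were followed, participant blinding could be compromised and the dose would differ from the one the visit procedure specifies. The conflict covers the full active arm (30 of 60 planned) and all 15 minutes of current per active participant.

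The conclusion assumes that the threshold in section 5.1.1 is the sensory one and that the stated intensity is the treatment intensity. Both are the natural readings, though not the only possible ones. The number of participants who would infer their allocation, and the size of any effect on the outcomes, cannot be derived from the protocol. Correction is needed before treatment starts, because a wrongly set current cannot be undone after the single test day.

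**What to change.** Reword the sentence in section 5.1.1 to say that sensory testing determines each participant's sensory threshold, that active stimulation is then set below it, and that the pain threshold is a safety ceiling only. Name the sensory threshold in section 3 as well, so that all three sections state the same rule. It would help to add how threshold testing is carried out in the sham arm.

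If suprathreshold stimulation is what is intended, correct sections 3 and 8.3.2 instead, and qualify the participant-blinding statements in sections 5.1.2 and 8.2.

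The essential change is one reworded sentence. Sample size, visits and measurements are unaffected.
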